1. SYNOPSIS

| | |
|---|--|
| Study Title | Intraoperative fetal heart rate (FHR) monitoring: a Feasibility Study |
| Objective | The introduction of intraoperative fetal heart rate (FHR) monitoring; demonstrating that intraoperative FHR monitoring is technically feasible. |
| Study Period | Planned enrollment duration: 6 months Planned study duration: 6 months |
| Number of Patients | 55 patients |
| Study Treatment | |
| Study Design | Observational Study |
| Inclusion and Exclusion Criteria | 
Inclusion Criteria:
 
 1. First 15 patients only— Elective induction of labor, not yet in active labor. 2. Subsequent 40 patient – Scheduled cesarean sections performed under spinal anesthesia 3. Patients ages 18-45 
Exclusion Criteria
 
 1. Urgent or emergent cesarean sections 2. Cesarean sections performed under general anesthesia |
| Statistical Methodology | Demographic, clinical characteristics will be summarized using descriptive statistics |

CONFIDENTIAL: This document is the intellectual property of [name]. Acceptance of this document constitutes the agreement by the recipient that no unpublished information contained herein will be published or disclosed without prior written approval.

2. STUDY PROTOCOL

2.1 Background and Significance

Fetal heart rate (FHR) monitoring has become the most widely used assessment of fetal well-being in the peripartum period and the only routinely used method that provides continuous fetal monitoring. Despite a false positive rate for the detection of intrapartum asphyxia leading to cerebral palsy of over 99% [1-3] FHR monitoring continues to be the mainstay of peripartum fetal surveillance. FHR monitoring is routinely available in the operating room, where it is typically reassessed in cases of urgent cesarean delivery for fetal distress since it may direct immediate anesthetic and peripartum management. However, despite the ubiquitous use of FHR monitoring in labor and the typical use of FHR monitoring on arrival to the OR, FHR monitoring is universally stopped once anesthesia has been performed in order to allow abdominal skin preparation and for surgery to proceed. From the moment of anesthesia induction until fetal delivery, no real-time data is available that allows assessment of fetal well-being. A few isolated studies and case reports in the 1970s-1980s examined intraoperative FHR monitoring using scalp-clip electrodes during Cesarean deliveries [4-7]. None of these studies assessed external FHR monitors or current anesthesia techniques. To our knowledge no studies since that time have examined FHR monitoring during Cesarean deliveries using external monitoring or spinal anesthesia.

2.1.1 Preliminary Data

None

2.2 Objective

The first objective of this study is the introduction of intraoperative fetal heart rate (FHR) monitoring as a novel fetal endpoint to be utilized in scheduled and urgent cesarean deliveries, in order to shed important light on the immediate fetal responses to maternal anesthetic and obstetric interventions. This research is intended to demonstrate that intraoperative FHR monitoring is technically feasible, and correlates with other traditional endpoints of immediate neonatal wellbeing (such as umbilical arterial blood gas analysis and Apgar score). Unlike these post-delivery neonatal outcomes, intraoperative FHR monitoring has the potential to serve as a real-time target for optimization of maternal and fetal condition in order to improve immediate neonatal outcome. We will first assess the fetal ECG monitors on a pilot of 15 patients for induction of labor who are not yet in active labor or in pain; the aim being to determine the best placement of the ECG leads. We will then assess the technical feasibility of intraoperative FHR monitoring using both the standard abdominal wall acoustic device used routinely in labor and a series of multiple ECG leads placed over the upper abdominal wall.

CONFIDENTIAL: This document is the intellectual property of [name]. Acceptance of this document constitutes the agreement by the recipient that no unpublished information contained herein will be published or disclosed without prior written approval.

DoCTR

2.3 Patient Selection

Patients enrolled in this study series will first be patients undergoing elective induction of labor (15 patients) and then patients undergoing elective cesarean delivery (40 patients.)

2.3.1 Inclusion Criteria

1. First 15 patients only– Elective induction of labor, not yet in active labor.
2. Subsequent 40 patient – Scheduled cesarean sections performed under spinal anesthesia
3. Patients ages 18-45

2.3.2 Exclusion Criteria

1. Urgent or emergent cesarean sections.
2. Cesarean sections performed under general anesthesia

2.4. Study Design

This will be an observational study to determine the feasibility of intraoperative FHR monitoring

2.4.1 Study Procedures

Patients enrolled in this study will be enrolled on the labor and delivery ward prior to their elective cesarean section. This will be done with the help of research assistants/nurses. Patients will be provided with written information about the study that they are enrolled in (see below) and consented for participation in the study as well as use of collected non-identifiable information; information on FHR (fetal heart rate) monitoring.

[figure not shown]
2.4.2 Minimization of Bias

The demographic sought in this study are female patients ages 18-45. No other particular demographic will be sought.

2.4.3 Pre-Study Period

The pre-study period will involve education of research assistants/nurses and anesthesiology providers, evaluation of availability of resources (includes BioSemi ECG, Fetal heart rate Doppler).

CONFIDENTIAL: This document is the intellectual property of [name]. Acceptance of this document constitutes the agreement by the recipient that no unpublished information contained herein will be published or disclosed without prior written approval.

2.4.4 Study Period

The study period is anticipated to be 6 months. This will start October 1st, 2016

Methods:

2.4.6 Observations and Measurements

This will be an observational study. We will first assess the fetal ECG monitors on a pilot group of patients for induction of labor who are not yet in active labor or in pain. We will then assess the technical feasibility of intraoperative FHR monitoring. Fetal heart rate will be assessed by:

a) External abdominal wall fetal ECG sensors placed at the top of the belly, outside the sterile field, or on the participant's back. This data is captured via BioSemi FLAT Active electrodes that interface with an ECG system that employs the algorithm ActiView to analyze the data. [See Appendix A].

[figure not shown]
b) An acoustic fetal heart sensor, as used routinely in labor will be used as a comparator in this feasibility study. When this device is used intraoperatively, sterility and acoustic contact are both maintained by placing the acoustic probe inside a sterile nylon sleeve containing electrode gel, and by using sterile electrode gel between the sterile sleeve and the abdominal wall. This technique may require the presence of an investigator "scrubbed into" the case to hold the abdominal wall probe (ie surgical scrub, sterile gown and gloves). This will be decided on a case-by-case basis. If needed, this investigator will need acoustic input to ensure adequate contact. So as not to distract the surgeon, this will be transmitted to the investigator by earphone input. These are scheduled cesarean deliveries and no fetal heart rate anomalies are expected; if there is an unexpected fetal bradycardia, this will be communicated to the surgeon.

c) Routine maternal vital signs (heart rate, blood pressure and oxygen saturation).

Group 1 – Patients for elective induction – not in active labor

- a) We will use the routine acoustic fetal heart rate sensor and try to determine the best placement of external abdominal wall fetal ECG sensors (either at the top of the belly outside the sterile field, or on the participant's back)
- b) We aim to capture 10 minutes of FHR with the ECG sensors comparing it to the acoustic monitor
- c) We will start with 5 patients. If we are able to capture FHR for the allotted period of time with the fetal ECG, then we will proceed to the intraoperative group. If not, we will assess another 5 elective induction patients.
- d) We will plan for an upper limit of 15 patients in this group

CONFIDENTIAL: This document is the intellectual property of [name]. Acceptance of this document constitutes the agreement by the recipient that no unpublished information contained herein will be published or disclosed without prior written approval.

Group 2 – Patients for scheduled cesarean section

- a) We will use the acoustic FHR sensor and the fetal ECG sensors.
- b) We will start with 5 patients and determine if we can capture fetal ECG. If this information correlates with the acoustic FHR, we then use only the fetal ECG sensors for the remaining 35 patients. We will adjust placement of leads for each group of 5 patient if there proves to be difficulty with capturing FHR intraoperatively, though all leads will be placed on the belly outside the sterile field or on the participant's back
- c) We will plan for an upper limit of 40 patients in this group

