2.4.6.4 Secondary Outcome Measures

Secondary endpoints are the incidence of any non-reassuring FHR patterns during the "silent" period which is the period when the FHR monitor is removed, the patient's abdomen is scrubbed, sterile prep and drape until delivery of the fetus. If there are any non-reassuring FHR patterns (tachycardia, bradycardia, decelerations), maternal vital signs at the time will be noted.

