3.2.2 Data Management

CONFIDENTIAL: This document is the intellectual property of [name]. Acceptance of this document constitutes the agreement by the recipient that no unpublished information contained herein will be published or disclosed without prior written approval.

Fetal heart rate recorded by external abdominal wall fetal ECG sensors is captured via BioSemi FLAT Active electrodes that interface with an ECG system that employs the algorithm ActiView to analyze the data.[See Appendix A]. .

With regard to confidentiality; 1) all subjects will be assigned a study ID number, 2) The link to identifiers will be destroyed at the end of the study 3) Paper data will be stored under lock and key (office, file cabinet) and only the investigators and research team will have access. Electronic data will be stored on a secure drive with limited individual password access. If data are published, there will be no link to identifiers. Study data will not be revealed to any organization, individuals other than the subjects, or the subjects themselves. 4) Maternal vital signs will be extracted from MetaVision and entered into a spreadsheet using only the study-specific ID. None of the 18 HIPAA identifiers will be recorded for research purposes.

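### No counting rule confirms that an ECG-derived rate is fetal, and the acoustic check may be dropped for 35 of the 40 cesarean patients

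*Combined protocol and SAP*

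**What the plan says.** All references are to the combined protocol and SAP.

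- **Lead position.** Section 2.4.6 (a): "External abdominal wall fetal ECG sensors placed at the top of the belly, outside the sterile field", or on the mother's back. The signal goes to "an ECG system that employs the algorithm ActiView to analyze the data". The readable text does not describe how maternal and fetal complexes are told apart.
- **Group 1 (induction).** Item (b) aims for 10 minutes of ECG-derived rate, compared with the acoustic monitor. Item (c) sets the condition for moving to the operating room: "If we are able to capture FHR for the allotted period of time with the fetal ECG". A captured trace is not defined.
- **Group 2 (cesarean).** Both sensors are used in the first 5 patients. If the two correlate, by a criterion that is not given, "we then use only the fetal ECG sensors for the remaining 35 patients".
- **Primary endpoint (2.4.6.3).** Ease of use, signal-to-noise ratio and correlation with the acoustic data. The text does not say whether maternal signal counts as noise.
- **Secondary endpoint (2.4.6.4).** The "incidence of any non-reassuring FHR patterns" in the interval before delivery when the usual monitor is off. Maternal vital signs are noted if such a pattern occurs. Tachycardia and bradycardia have no numeric thresholds.
- **Maternal data.** Section 2.4.6 (c) lists "Routine maternal vital signs (heart rate, blood pressure and oxygen saturation"), and section 3.2.2 adds: "Maternal vital signs will be extracted from MetaVision".
- **Analysis (2.4.6.5).** Descriptive summaries and an ROC comparison of the two methods, with no check on the source of the signal.

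**The concern.** The study sets out to show that these leads measure the heart rate of the fetus. Whose heart is being tracked is therefore part of feasibility itself. Electrodes on the mother's trunk can record her heart as well, and the plan has no rule that uses maternal heart rate to decide whether a trace is counted.

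Three errors are possible:

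1. A stretch of maternal signal is scored as captured fetal rate, and feasibility looks better than it is.
2. A resting maternal rate is scored as fetal bradycardia, and the secondary incidence is too high.
3. A fast maternal rate is read as a normal fetal rate. It counts as captured, no pattern is flagged, and any true fetal event at that time is missed.

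The ECG-only cesarean patients matter most. They would supply most of the data for the secondary endpoint, and they have no second fetal signal.

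**Working it through.** **The plan's own figure.** Section 2.4.6.6 gives 55 patients. The group limits in section 2.3 give 15 + 40 = 55, so the figure is reproduced. It has no statistical derivation, and this point needs none.

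**Who has an independent fetal reference**

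- Group 1: 5 to 15 patients. Group 2: the first 5. Total: 5 + 5 = 10 to 15 + 5 = 20.
- Group 2 without a reference, if the switch is made: 40 − 5 = 35, and 35/40 = 87.5%.

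**Which safeguard meets which error in the ECG-only patients**

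| Error | Is the maternal note in 2.4.6.4 triggered? | Does a rule change what is counted? |
|---|---|---|
| Maternal rate scored as fetal bradycardia | Yes | No: it is a record only |
| Maternal rate read as a normal fetal rate | No | No |
| Maternal segment scored as captured | Only if a pattern is also seen | No |

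**Sensitivity, on assumed heart rates.** The documents give no rates or thresholds. Assume a maternal rate of 70–100 bpm, a normal fetal rate of 110–160 bpm, and bradycardia below 110 bpm.

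- Every maternal segment in that range would then look like bradycardia and would trigger the note. The second row of the table needs a maternal rate of at least 110 bpm, which lies outside the assumed range. How often that occurs in this population is not stated.
- With fetal 140 and maternal 90 bpm, and 10% of the trace taken from the mother, the mean recorded rate falls by 0.10 × (140 − 90) = 5 bpm.
- Each patient wrongly counted with a pattern adds 1/40 = 2.5 percentage points if all 40 are evaluable; four add 4/40 = 10 points.

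**Could the first 5 cesarean patients reveal the problem?** Let p be the chance that the ECG tracks the mother in a given patient, independently between patients. P(at least one in n) = 1 − (1 − p)^n. The values of p are assumed.

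| p | First 5 | 35 ECG-only | Expected among 35 (35 × p) |
|---|---|---|---|
| 0.02 | 0.096 | 0.507 | 0.7 |
| 0.05 | 0.226 | 0.834 | 1.75 |
| 0.10 | 0.410 | 0.975 | 3.5 |
| 0.20 | 0.672 | above 0.99 | 7 |

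At the lower values of p, the first 5 patients would probably show no such case, while the 35 would more likely than not include at least one. This illustrates the limit of a 5-patient check; it does not forecast a rate.

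**The case against.** The strongest reply is that the plan already has two safeguards.

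- **The acoustic monitor.** Group 1 capture is compared with it, the Group 2 switch requires correlation with it, and that correlation is part of the primary endpoint. A trace at the maternal rate should disagree with the acoustic rate. This stands for 10 to 20 patients, although the agreement criterion is undefined. It does not reach the 35.
- **The maternal note.** Maternal vital signs, including heart rate, are noted at each flagged pattern. This also stands: an apparent bradycardia can be looked at again with planned data. What is missing is a rule for what the comparison does to the count, and any trigger when the rate looks normal.

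A reader might go further in four ways that the documents do not support:

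- *That the planned data cannot separate mother from fetus in the ECG-only patients.* For apparent bradycardia they can, because of the note.
- *That the acoustic probe may itself follow the mother's pulse.* The documents say nothing on this, so it cannot be used to discount the comparator.
- *That the software does not separate the two signals.* The plan is silent, and a figure beside that text is not reproduced in the copy reviewed. ActiView may do so; the plan states no check that it does.
- *That capture or incidence will be inflated by a given amount.* No misattribution rate is given.

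A further fair objection concerns the remedy. Deleting every segment near the maternal rate would also delete true fetal bradycardia at that rate and break up decelerations that cross it, which would bias the secondary incidence downward. The fix has to avoid this. Nor do the documents state how often maternal heart rate is recorded, so close time-matching cannot be assumed.

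**Conclusion.** The gap is real but narrower than it may first appear. No readable text says how an ECG-derived rate is confirmed as fetal. The acoustic comparator is a partial check that may end after the first 5 cesarean patients, leaving 35 of 40 (87.5%) without it. For those patients the remaining check is maternal heart rate. It is noted only when a non-reassuring pattern is seen, and it decides nothing about what is counted. A maternal rate read as a normal fetal rate would pass as captured without any note.

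The size is unknown. The 5 bpm shift, the 2.5 points per patient and the table of chances all depend on assumed inputs and show sensitivity only. The conclusion rests on one inference that the documents do not state, that leads on the mother's trunk can record her heart, and on the 35-patient switch being made. The change is worth making because it bears on the study's central claim and uses data already planned.

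**What to change.** Amend section 2.4.6 (the general measurements and both group procedures) and section 2.4.6.4:

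1. Compare each ECG-derived rate with the concurrent maternal heart rate already collected, at the resolution at which it is recorded, and state that resolution.
2. Pre-specify a coincidence criterion (for example, within 5 bpm; the width is the sponsor's to justify) and label segments that meet it *source uncertain*.
3. Where an acoustic trace exists, use it to resolve the label.
4. Do not count unresolved segments as confirmed capture in either group, and report their share of recorded time.
5. Report the incidence of non-reassuring patterns both including and excluding source-uncertain segments, so that true fetal events at or crossing the maternal rate are not silently removed.

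The cost is protocol wording, a little more trace review, a slightly less favourable capture figure, and a range in place of a single incidence. No new data collection is required. The change concerns analysis only and proposes nothing about what is communicated or done during surgery.

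### The silent-period incidence counts fetal heart rate patterns that were already present, and the plan records nothing about fetal condition that would let them be separated

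*Combined protocol and SAP*

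**What the plan says.** **Eligibility.** Section 2.3.1, repeated in the Synopsis, admits two groups: "Elective induction of labor, not yet in active labor" for the first 15 patients, and "Scheduled cesarean sections performed under spinal anesthesia" for the next 40. Both must meet "Patients ages 18-45". Section 2.3.2 excludes "Urgent or emergent cesarean sections" and "Cesarean sections performed under general anesthesia". Section 2.4.2 adds that "No other particular demographic will be sought" beyond sex and age.

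**Expectation about the fetus.** The only statement is in Section 2.4.6, in the paragraph on the acoustic probe: "These are scheduled cesarean deliveries and no fetal heart rate anomalies are expected". The same sentence goes on to say that an unexpected bradycardia will be reported to the surgeon.

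**Secondary endpoint.** Section 2.4.6.4 reads "Secondary endpoints are the incidence of any non-reassuring FHR patterns during the" silent period, which runs from taking the monitor off until delivery. It names three kinds of pattern (bradycardia, tachycardia, decelerations) and asks for the maternal vital signs at the time of each.

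**Purpose and analysis.** Section 2.2 wants intraoperative monitoring to reveal how the fetus reacts straight away to anesthesia and obstetric procedures. Section 2.4.6.5 plans descriptive statistics and a ROC comparison of the two monitors.

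**The concern.** That a cesarean is scheduled says when it happens, not that the fetus has a normal heart rate. Section 3.3 treats elective and non-urgent as equivalents for cesareans, so elective does not fill the gap either. A delivery may be scheduled for a fetus whose rhythm disorder is already known, and nothing in the criteria keeps that patient out.

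The endpoint then has no means of telling such a case from a fetus whose heart rate changed after the monitor came off. Both are one event over the same denominator. What is at stake is the meaning of the secondary incidence: a reader will take it as what happens to fetuses during an interval that is normally unmonitored, and part of it may be what was there beforehand. Where few or no events are expected, one such case could be the whole result.

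**Working it through.** **1. The plan's own figure.** Section 2.4.6.6 gives 55 patients: 15 inductions + 40 cesareans = 55, which reproduces. It gives no event rate or precision target, so there is nothing further to reproduce.

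**2. Does any criterion concern the fetus?**

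| Criterion | What it restricts |
|---|---|
| Induction group, Section 2.3.1 | Type of delivery, stage of labor |
| Cesarean group, Section 2.3.1 | Scheduling, type of anesthesia |
| Age, Section 2.3.1 | The mother |
| Exclusion 1, Section 2.3.2 | Urgency |
| Exclusion 2, Section 2.3.2 | Type of anesthesia |

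None does so directly. Exclusion 1 removes some acute fetal compromise, but not a chronic disorder in a scheduled case. Section 2.5.2 allows withdrawal in the interest of fetus or mother; that is discretionary and is not a screen at entry.

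**3. What must be true for a pattern to count?** Under Section 2.4.6.4 it must be one of the named kinds and occur in the window. There is no comparison with an earlier tracing, no requirement that it be new, and no rate or duration threshold. Section 2.4.6.5 adds no analysis that separates old from new.

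**4. Can it be separated afterwards?** Section 3.2 lists the data drawn from the record: fetal heart rate, blood pressure, vasopressor dose, cardiac output and fetal blood gases. Cesarean indication and fetal diagnosis are not listed. Section 3.2.2 destroys the link to identifiers at study end, so after that point a field not collected cannot be recovered from the chart.

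**5. Size of one case.** The denominator is at most 40 (Section 2.4.6, Group 2). One case adds 1/40 = 0.025, or 2.5 percentage points. Exact (Clopper-Pearson) 95% intervals:

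- 0/40: the lower limit is 0; the upper limit is 1 − 0.025^(1/40) = 0.088. Interval 0 to 8.8%.
- 1/40: the lower limit is 1 − 0.975^(1/40) = 0.0006; the upper limit solves (1 − p)^40 + 40p(1 − p)^39 = 0.025, giving p = 0.132. Interval 0.1 to 13.2%.

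**6. How likely is at least one?** The documents give no frequency, so the values of p below are assumptions. Here p is the proportion of scheduled cesareans in which a known condition shows as one of the named patterns. The chance of at least one among 40 is 1 − (1 − p)^40, and the expected number is 40p.

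| Assumed p | Chance of at least one | Expected number |
|---|---|---|
| 0.5% | 18% | 0.2 |
| 1% | 33% | 0.4 |
| 2% | 55% | 0.8 |
| 5% | 87% | 2.0 |

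The range is wide because the input is unknown. It shows only that the possibility cannot be dismissed at this sample size.

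**The case against.** The strongest reply is that the endpoint is not wrong as written. It counts any pattern in the window and attributes no cause, so a pre-existing bradycardia seen in that window meets the definition. The primary endpoint (Section 2.4.6.3) is technical, and the incidence is secondary and descriptive. This stands, and it limits the point to what the incidence can be taken to show. It does not remove the point, because Section 2.2 gives the reason for looking as the fetal response to interventions.

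Three stronger readings are tempting, and the documents do not support them.

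- *A reader might infer that the plan rests on a formal assumption of normal fetal heart rates.* The sentence is an operational remark in a passage about communication with the surgeon. No criterion or analysis is built on it.
- *A reader might infer that one such fetus could decide a five-patient step in Section 2.4.6.* Those steps ask whether the heart rate can be captured and, in Group 2, whether it correlates with the acoustic signal. There is no per-patient scoring rule or threshold, and an abnormal rate can still be captured. The documents also do not say how the ECG software derives a rate, so disagreement between the monitors in an irregular rhythm is not shown.
- *A reader might infer that such fetuses must be excluded.* A broad exclusion would narrow the range of heart rates available for the correlation in Section 2.4.6.3 and remove abnormal cases that the ROC comparison in Section 2.4.6.5 would use. It would also take in structural heart defects that never alter the rate.

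It is also fair to say that the 0/40 and 1/40 intervals overlap almost entirely, and that the number of affected fetuses is probably small.

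**Conclusion.** The concern holds as a small, inexpensive improvement. The criteria do not address fetal condition and the secondary endpoint does not distinguish existing from new patterns, so a known disorder that alters the heart rate would be reported as a silent-period event. The size is 2.5 percentage points per case on a denominator of 40. It would be somewhat larger per case if fewer than 40 patients yield a usable recording.

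This rests on two assumptions: that at least one such patient is enrolled, and that the condition shows as one of the named patterns during the window. Rhythm disorders are the direct case; a structural defect matters only if it alters the rate. The primary endpoint, the stepwise decisions and the total of 55 are not called into question.

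**What to change.** For each Group 2 patient, record three things: any known fetal diagnosis expected to alter the heart rate, the indication for the cesarean, and the pattern on the tracing just before the monitor is removed. Section 2.4.6.4 defines its window by that removal, and Section 2.1 describes monitoring on arrival in the operating room as typical, so a tracing should usually exist. Add the three items to the data list in Section 3.2 and collect them during the study, before the identifier link is destroyed.

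In Section 2.4.6.4, report patterns that are new in the silent period separately from those already present, and show the incidence with and without patients who have such a diagnosis. Label the second category as present before monitor removal, not before anesthesia: Section 2.1 describes the monitor as coming off after anesthesia, so a pattern on that tracing may already reflect it.

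An exclusion criterion is optional. If one is used, limit it to known fetal rhythm disorders, state it in both the Synopsis and Section 2.3.2, and accept that the results then do not cover such fetuses.

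The cost is a few extra recorded fields and a slightly longer table. The sample size and the other stated figures do not change. The documents do not confirm that the indication is readily available in the record, so this should be checked before the field is added.

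### Group 2 moves 35 of 40 patients to fetal ECG alone on capture and correlation in 5 cases that will often contain no abnormal episode, so a low count of non-reassuring patterns could reflect non-detection

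*Combined protocol and SAP*

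**What the plan says.** Group 2 in section 2.4.6 begins with both sensors: "We will start with 5 patients and determine if we can capture fetal ECG". The next sentence sets the switch: "If this information correlates with the acoustic FHR, we then use only the fetal ECG sensors for the remaining 35 patients". The group is capped at 40. The rule thus has two conditions, capture and correlation. It gives no coefficient, cut-off or unit of analysis, and it does not mention detection of episodes. If capture proves difficult, leads are adjusted for each group of 5.

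The same section says of this population: "These are scheduled cesarean deliveries and no fetal heart rate anomalies are expected". Section 2.3.2 excludes "Urgent or emergent cesarean sections".

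Section 2.4.6.4 reads: "Secondary endpoints are the incidence of any non-reassuring FHR patterns during the 'silent' period". It names what is counted: "If there are any non-reassuring FHR patterns (tachycardia, bradycardia, decelerations), maternal vital signs at the time will be noted".

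Two other provisions bear on the point. Group 1 (up to 15 induction patients not in active labor) aims at 10 minutes of ECG capture compared with the acoustic monitor. Section 2.4.6.5 plans a ROC curve to compare the two monitors.

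**The concern.** Whether the ECG follows a normal baseline and whether it shows a deceleration, bradycardia or tachycardia are different questions. The switch addresses the first, and the secondary endpoint needs the second. If the 5 paired traces hold only normal readings, an ECG that shows episodes and one that does not produce the same paired data, and no correlation cut-off can tell them apart.

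After the switch there is no second trace. A low or zero count in the 35 could then mean that the silent period was quiet or that the sensor missed the episodes, and the data would not say which. Section 2.2 presents intraoperative FHR as a new fetal endpoint and a possible real-time target, so the distinction bears on the study's purpose.

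**Working it through.** **The plan's own figures.** 15 + 40 = 55 and 5 + 35 = 40, as stated. ECG-only share of Group 2: 35/40 = 87.5%.

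**Inputs.** From section 2.4.6: 5 paired cases and 35 ECG-only cases. Not in the documents: the per-patient episode rate p, assumed here to be 2% to 20%.

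**Step 1: can the paired cases contain an episode?** P(none in 5) = (1 − p)^5. A zero count in the 35 with a perfect sensor has probability (1 − p)^35. The expected number of patients with an episode among the 35 is 35p.

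| p | None in the 5 | Expected in the 35 | Zero in the 35, perfect ECG |
|---|---|---|---|
| 2% | 0.98^5 = 90% | 0.7 | 49% |
| 5% | 0.95^5 = 77% | 1.75 | 17% |
| 10% | 0.90^5 = 59% | 3.5 | 2.5% |
| 20% | 0.80^5 = 33% | 7 | under 0.1% |

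The chance of no episode in the 5 exceeds 50% while p < 1 − 0.5^(1/5) = 12.9%. Seeing 0 of 5 leaves a one-sided 95% upper limit on p of 1 − 0.05^(1/5) = 45%, so a quiet start does not show that episodes are rare. If lead adjustment extends pairing to 10 cases, the chance of none is still 60%, 35% and 11% at p = 5%, 10% and 20%.

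**Step 2: what does correlation do if an episode occurs?** This was simulated, and every input is an assumption: 5 patients, 20-minute records read every 5 seconds, between-fetus SD 10 bpm, within-fetus SD 6 bpm (autocorrelation 0.95), device noise SD 2 bpm, and an episode that is a 40 bpm fall for 2 minutes. Percentages are trials that pass when r is averaged over the 5 fetuses. Repeat runs differ by a few points.

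| ECG behavior, criterion | p = 5% | p = 10% | p = 20% |
|---|---|---|---|
| Stays at baseline, mean r ≥ 0.7 | 97% | 93% | 78% |
| Stays at baseline, mean r ≥ 0.8 | about 82% | about 67% | 43–45% |
| Shows the episode, mean r ≥ 0.8 | over 99% | over 99% | over 99% |
| Drops out, unreadable pairs excluded, mean r ≥ 0.8 | over 99% | over 99% | over 99% |

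At mean r ≥ 0.9, an ECG that shows episodes passes in 15–37% of trials over p = 5–20%, against 2–5% for one that stays at baseline. That cut-off does separate them, but it also rejects most sound sensors under the assumed noise.

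**Step 3: how much depends on the method of calculation?** With exactly one episode among the 5, the baseline-holding ECG passes mean r ≥ 0.7 in about 95% of trials, but passes r ≥ 0.7 in every fetus in only 2–3%. Pooling all readings is more lenient for short episodes. In separate runs (autocorrelation 0.9), pooled r ≥ 0.8 was reached in 95–100% of trials for 60-second, 30 bpm falls at p = 5–30%. For 180-second, 40 bpm falls it was reached in 88%, 76% and 59% at p = 5%, 10% and 20%. The wording of the rule allows any of these readings.

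**The case against.** A reader might infer that the rule cannot distinguish an ECG that shows episodes from one that misses them. The figures do not support that. At p = 20% and mean r ≥ 0.8, the first passes in over 99% of trials and the second in 43–45%. A requirement in each fetus, natural with five traces, would expose a baseline-holding ECG in nearly every trial with an episode. What stands is that this needs an episode among the 5.

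A reader might also take the dropout result as unconditional. It holds only if unreadable pairs are excluded and the lost signal is not treated as a failure of capture. Capture is itself a condition of the switch, signal-noise ratio is part of the primary endpoint (section 2.4.6.3), and a gap in an ECG-only trace is visible as missing data. The plan sets no standard for how much loss counts as failed capture, so the possibility remains, but it is conditional.

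Nor is it fair to say that detection is tested nowhere. A ROC curve needs a binary state and so points toward classification, and Group 1 adds 5 to 15 paired recordings. Neither closes the gap: neither is part of the Group 2 switch rule, no reference event is defined for the ROC, and Group 1 proceeds on capture.

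Finally, no passage says that a low count will be presented as reassuring. This is a descriptive feasibility study and the endpoint is secondary. That limits the weight of the point; it does not resolve how the count should be read.

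**Conclusion.** The concern holds in a limited form. Episode detection is not a condition for moving 35 of 40 patients to ECG alone, and the 5 cases used to decide will often contain nothing to detect: no episode in more than half of studies for any per-patient rate below about 13%. The switch is then a weak test of what section 2.4.6.4 counts, and a low or zero ECG-only count is ambiguous. At assumed rates of 5% to 20%, 1.75 to 7 of the 35 patients would be expected to have an episode that a non-detecting sensor would miss.

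The no-episode probabilities rest only on the assumed rate and on independence between patients. The pass rates also rest on the assumed trace model, the cut-off and the averaging, none of which the plan states. The claim that a non-detecting ECG would usually pass fails when episodes are frequent and the criterion is strict. The documents support a weak test, not a useless one, and the consequence is confined to a secondary endpoint.

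**What to change.** 1. **Score episodes on every paired recording** (Group 1 and the paired Group 2 cases). Classify each tachycardia, bradycardia or deceleration on the acoustic trace as shown, not shown or unreadable on the ECG, and score episodes seen only on the ECG in the same way. Report positive agreement with an exact interval, counting unreadable as not shown. Use this scoring as the binary reference for the ROC comparison in section 2.4.6.5.

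2. **Limit what the switch supports.** State in Group 2(b) that correlation supports ECG-only use for baseline rate. Report the section 2.4.6.4 result separately for paired and ECG-only patients, each with the readable share of the silent period. Label the ECG-only result *episodes seen on ECG, detection not verified* unless a pre-stated minimum number of paired episodes and a pre-stated lower limit of positive agreement are both met. A minimum is needed because one episode shown out of one has an exact 95% interval of 2.5% to 100%. Unless the standard is met, draw no conclusion from a low or zero count.

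The cost is a few sentences of protocol text and a review of traces already being recorded, with no added patients, staff or procedures. The fix leaves the number of unpaired patients unchanged. If few or no paired episodes occur, the secondary endpoint carries a weaker claim.
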